11.2. Observation Items and Methods

11.2.1. Acquisition of Informed Consent

The investigator should explain in detail the purpose and contents of the study to the subjects who intend to participate in this study. The subject confirms the information about the study, and signs the informed consent form by hand. The informed consent must be obtained prior to performing all procedures associated with the study. After receiving the informed consent of the subject, the investigator will give the screening number in the order of participation in the study.

11.2.2. Demographic Survey

During the screening visit, a demographic survey on the status of the informed consent, date of consent, subject's initial, gender, date of birth, weight, height, BMI, smoking and drinking status, etc. is conducted. At Visits 3, 4, 5, 6 and at the time of early termination/dropout, only the body weight is measured.

11.2.3. Medical History/Prior Surgery

A detailed examination and recording of medical history and prior surgery of the subjects are carried out through a medical examination by interview and by reviewing past medical records. For the medical history including surgical operations, allergies, etc., name of the diagnosis/surgery, status of continuation, etc. are recorded. For other baseline characteristics, information on histological findings of gastric cancer (including TNM stage), types of gastrectomy, types of reconstruction, lymph node dissection, etc. is collected.

11.2.4. Physical Examination and Vital Signs

Physical examinations will be conducted at Visits 1, 4 and 6 or at the time of early termination/dropout. The investigator will perform the physical examination through interviewing, examining, facilitating, and stethoscoping, etc. of subjects, and the result is recorded on the case record form. Test items include general appearance, skin/mucosa, lymphatic system, cephalus/cervical part, eye/ear/nose/ throat, gastrointestinal, cardiovascular, respiratory, neurological and musculoskeletal systems. And, symptoms due to the underlying disease of this study will not be collected.

Vital signs (blood pressure, pulse) are measured at each visit. Pulse and blood pressure should be measured after the subject has been sitting for 5 minutes, and always on the same arm for evaluation.

11.2.5. Abdominal Ultrasound

Abdominal ultrasound is performed at Visits 1 (baseline), 3, 4, 5 and 6, or at the time of early termination/withdrawal to determine gallstone formation. At Visits 3 and 6, the abdominal ultrasound should be performed prior to the upper gastrointestinal endoscopy. Also, if abdominal ultrasound is performed on the same day as abdominal CT scan, the abdominal ultrasound should be performed prior to abdominal CT scan. Patients should remain in a fasting state for at least 8 hours before the test up until the end of the test. If the patient is unable to do so, the visit process should stop to reschedule it. If it is difficult to perform abdominal ultrasound on the regular visit due to the testing schedule of each study site, it may be done within regular visit ± 2 weeks.

The investigator confirms through abdominal ultrasound whether gallstones have formed in areas including the liver, gallbladder, and bile ducts. If gallstone formation is confirmed, an ultrasound

Confidential Page 25 of 51

photograph that confirms the formation of gallstones should be stored as an evidence document. Even if gallstone formation is not confirmed, ultrasound photographs that are available for the following four sites should be kept as an evidence document.

- 1) A subcostal scan that allows monitoring both portal veins
- 2) An intercostal scan that allows monitoring the right portal vein
- 3) A subcostal scan that allows monitoring the full length of the gallbladder
- 4) An intercostal scan that allows monitoring the full length of the gallbladder

11.2.6. Abdominal CT Scan

An abdominal CT scan is performed at Visit 1 (baseline), Visit 4 and Visit 6. Patients should remain in the fasting state for at least 8 hours before the test. If the patient is unable to do so, the visit process should stop to reschedule it. If it is difficult to perform the abdominal CT scan on the day of a regular visit due to the test schedule of each study site, it can be performed within regular visit ±2 weeks.

The investigator obtains pre-contrast and post-contrast abdominal CT images and confirms gallstone formation in the liver, gallbladder, and bile ducts.

In this case, if the investigator judges that the CT scan of parts including the liver, gallbladder, and bile duct, is enough to identify gallstones, the CT scan of parts other than the abdominal CT (e.g., stomach CT, whole body CT, etc.) can also be used in place of the abdominal CT.

11.2.7. Determination of Gallstones

The diagnosis of gallstone formation is based primarily on the results of the abdominal ultrasound and is supplemented by abdominal CT scan results. If the results of the two tests differ, abdominal ultrasound result should be considered first for gallbladder gallstones, and both abdominal ultrasound and abdominal CT should be considered in the case of bile duct gallstones or intrahepatic bile duct gallstones.

If the abdominal ultrasound results satisfy the following criteria, it will be considered as a gallstone in the gallbladder. ^{9),,25)-28)} If any one of the criteria is not met, or there is only hyperechoic shadow without posterior acoustic shadow, it is judged as negative for gallstone formation.

- 1) Hyperechoic shadow (echo sign)
- 2) Posterior acoustic shadow
- 3) The movement of echo according to changes in body position (movement, gravitational dependence)

The bile duct gallstone is distinguished by abdominal ultrasound that shows a hyperechoic substance with posterior acoustic shadow or an enlargement of peripheral bile duct around the echo, and is determined by compiling the results of abdominal CT scans.

Gallstones should be distinguished from biliary sludge and should be determined to be biliary sludge if the following criteria are met:

- 1) Hypoechoic shadow without accompanying acoustic shadow
- 2) Moves according to changes in body position and has a characteristic to form a horizontal plane

The investigator will document in the case record form (CRF) the presence of gallstones, the presence of biliary sludge, and the location of gallstones (gallbladder, common bile duct, intrahepatic bile duct), size and number of gallstones.

Confidential Page 26 of 51

11.2.8. External Investigator's Assessment of the Imaging Test Results for Gallstone Formation

To ensure the reliability of the imaging test results (abdominal ultrasound and abdominal CT scan), independent external investigators evaluate the results of imaging tests to determine whether gallstones have formed. External investigators consist of three independent investigators who have not participated in the corresponding clinical study.

The external committee member will independently check the results of the imaging test without any exchange of opinions and state whether gallstones have formed or not. The assessment is based on abdominal ultrasound and CT imaging data collected from all study sites and is randomly arranged regardless of the number or the order of the visit of the subjects so that researchers can conduct an assessment without being affected by the time of shooting. The assessment results on which at least two of the three external investigators agree on will be selected.

11.2.9. Assessment of Biliary Reflux Symptoms and Upper Gastrointestinal Endoscopy

The assessment of symptoms for a biliary reflux will be conducted at Visits 2 (baseline), 3, 4, 5 and 6, or at the time of early termination/withdrawal to determine the gallstone formation. The subjects completes a questionnaire (Appendix 2) in three areas including the frequency, strength, and the level of pain of the representative symptoms of biliary reflux (upper abdominal pain, heartburn, and nausea).

In addition, the investigator will perform an upper gastrointestinal endoscopy at Visits 3 and 6 to confirm the actual reflux of bile and record the results. There is no need for a separate endoscopy, but endoscopy results under routine clinical practices can be collected and used.

To diagnose bile reflux during the upper gastrointestinal endoscopy, the investigator will evaluate the status of bile reflux (Y/N) by observing the remnant stomach or the anastomotic area and determine it as bile if a yellow liquid is observed in the assessed area. If bile reflux is observed, gastritis is assessed as well according to the following criteria: ^{29),30)}

- 1) Grade 0: No flare on mucous membrane or the remnant stomach or anastomotic area.
- Grade 1: Mild redness is observed in the mucous membrane of the remnant stomach or anastomotic area.
- 3) Grade 2: A comb-shaped redness is observed on mucous membrane of the remnant stomach or anastomotic area.
- 4) Grade 3: Severe redness and edema are observed on mucous membrane of the remnant stomach or throughout the anastomotic area.

[figure not shown]
11.2.10. Laboratory Tests

Laboratory tests are carried out using the Central lab and are performed in a fasted state at Visits 1, 4 and 6 or at the time of early termination/withdrawal. If screening results do not meet the inclusion/exclusion criteria, they may be retested only once. Women of childbearing age should be checked for pregnancy through a urine hCG test at Visit 1. In addition, if it is deemed necessary based on the investigator's judgment, additional tests may be conducted.

Laboratory test items are as follows:

Hematology	WBC, RBC, Hemoglobin (Hb), Hematocrit (Hct), Platelet count, WBC differential count
	(Neutrophil, Lymphocyte, Monocyte, Eosinophils, Basophils)

Confidential Page 27 of 51

Biochemical test	Glucose, Total protein, Albumin, Total cholesterol, Triglyceride, Total bilirubin, alanine transaminase (ALT), aspartate transaminase (AST), alkaline phosphatase (ALP), blood urea nitrogen (BUN), gamma-glutamyl transferase (γ-GTP), Uric acid, Creatinine, sodium, potassium, chloride, calcium, HbA1c*, eGFR
Urinalysis	Bilirubin, urobilinogen, Blood, Glucose, pH, Protein, Specific Gravity
Pregnancy test**	Urine HCG

[†] HbA1c: It will be performed once at screening, and if there is a test result within the last 3 months, it can be replaced with the screening test result.

In addition, only the liver function tests (ALT, AST, ALP, y-GTP and total bilirubin) among the biochemical tests are performed at Visits 3 and 5.

11.2.11. Adverse Events

The investigator will be trained to voluntarily report from time to time when an adverse event occurs to the subject. In addition, the investigator should check the occurrence of the adverse events through consultation and interviews at regular visits during the study period.

The investigator should review the results of the laboratory tests and evaluate whether the results diverging from the normal value are clinically significant. If it is considered that there is a clinical significance when before and after the administration of the investigational product are compared, it should be evaluated as an adverse event. Also, based on the physical examination results, significant changes in the physical examination findings which are consistent with the definition of an adverse event after the administration of the investigational product should be also assessed as an adverse event.

Investigation of adverse events includes the dates of onset and disappearance, severity, treatment, outcomes, causal relationship with the investigational product, actions taken in relation to the investigational product, suspected drugs other than the investigational product and seriousness, etc.

11.2.12. Prior/Concomitant Medications

The investigator should be aware of the drugs that are allowed and prohibited for concomitant use in this study, investigate drugs used concomitantly by subjects, and confirm whether the study protocol is followed.

To identify prior medications, the information (product name or ingredient name, purpose of administration, dose, duration of administration, etc.) of the drugs administered within 4 weeks based on the screening visit should be investigated. In addition, changes in concomitant drugs should be confirmed at every visit, and the changes should be recorded in the case record form.

11.2.13. Prescription of Investigational Products and Treatment Compliance

Subjects who meet the inclusion criteria and do not correspond to the exclusion criteria are randomly assigned to the study arm or the control group at Visit 2 to receive the investigational product. The investigator will prescribe the investigational products with a quantity of approximately 3 months + 1 week (99 days) taking into account the next visit schedule at Visits 2, 3, 4 and 5. And, at Visits 3, 4, 5, 6 or visits for the early termination/withdrawal, the unused portion of the investigational products that are prescribed in previous visits will be collected from subjects to verify the treatment compliance. Subjects whose treatment compliance does not exceed 85% will receive retraining for the administration of investigational products.

Confidential Page 28 of 51

^{**} Pregnancy test: It is performed only for women of childbearing age.

11.3. Visit Schedule

11.3.1. Visit 1 (screening, Week - 2)

The subjects who are scheduled to participate in this clinical study will hear explanations about the study from the investigator and perform screening visits according to the following procedure: The investigator will use the information obtained from Visit 1 to determine if the subject is eligible to participate in the study.

- The informed consent will be obtained from subjects before the study procedures, and the screening number will be distributed.
- Demographics are collected.
- Information about the medical history/prior surgery is collected.
- Information on prior/concomitant medications is collected.
- A physical examination is carried out.
- Vital signs (blood pressure, pulse) are measured.
- Laboratory tests (hematology, biochemistry, urinalysis) are carried out.
- For women of childbearing age, a pregnancy test is carried out.
- Abdominal ultrasound is performed to confirm the presence of gallstones.
- Abdominal CT scan is performed to confirm the presence of gallstones.
- The inclusion/exclusion criteria are verified.
- The subsequent visit dates are determined.

11.3.2. Visit 2 (randomization and administration of investigational products, Day 1)

Visit 2 will take place within two weeks after the screening (Visit 1). If the subject is suitable for participating in the clinical study, the following procedures will be performed:

- Vital signs (blood pressure, pulse) are measured.
- Changes in the medication history and therapeutic potential are checked compared to previous visits.
- Changes in the medical history/prior surgery are checked compared to previous visits.
- The inclusion/exclusion criteria are re-verified.
- Randomization is performed.
- Investigational products are prescribed, and guidance is provided for taking medications.
- A questionnaire to evaluate the symptoms of biliary reflux is prepared.
- The subsequent visit dates are determined.

11.3.3. Visit 3 (treatment period, 3 months ± 1 week)

At visit 3, the following procedures will be performed at 3 months ± 1 week after Visit 2.

- Among the demographic survey, only the body weight is measured.
- Vital signs (blood pressure, pulse) are measured.
- Changes in the medication history and therapeutic potential are checked compared to previous visits.
- Adverse events are checked.
- Abdominal ultrasound is performed. It should be performed prior to upper gastrointestinal endoscopy.
- Upper gastrointestinal endoscopy is performed to check bile reflux.

Confidential Page **29 of 51**

- A questionnaire to evaluate the symptoms of biliary reflux is prepared.
- Among laboratory tests, liver function tests (ALT, AST, ALP, γ-GTP and total bilirubin) are performed.
- Unused medicinal products are collected, and treatment compliance is checked.
- Investigational products are prescribed, and guidance is provided for taking medications.
- The subsequent visit dates are determined.

11.3.4. Visit 4 (treatment period, 6 months ± 1 week)

At Visit 4, the following procedures will be performed at 3 months ± 1 week after Visit 2.

- Among the demographic survey, only the body weight is measured.
- A physical examination is carried out.
- Vital signs (blood pressure, pulse) are measured.
- Changes in the medication history and therapeutic potential are checked compared to previous visits.
- Adverse events are checked.
- Abdominal ultrasound is performed. It should be performed prior to abdominal CT scan.
- Abdominal CT scan is performed.
- A questionnaire to evaluate the symptoms of biliary reflux is prepared.
- Laboratory tests (hematology, biochemistry, urinalysis) are carried out.
- Unused medicinal products are collected, and treatment compliance is checked.
- Investigational products are prescribed, and guidance is provided for taking medications.
- The subsequent visit dates are determined.

11.3.5. Visit 5 (treatment period, 9 months ± 1 week)

At Visit 5, the following procedures will be performed at 9 months ± 1 week after Visit 2.

- Among the demographic survey, only the body weight is measured.
- Vital signs (blood pressure, pulse) are measured.
- Changes in the medication history and therapeutic potential are checked compared to previous visits.
- Adverse events are checked.
- Abdominal ultrasound is performed.
- A questionnaire to evaluate the symptoms of biliary reflux is prepared.
- Among laboratory tests, liver function tests (ALT, AST, ALP, γ-GTP and total bilirubin) are performed.
- Unused medicinal products are collected, and treatment compliance is checked.
- Investigational products are prescribed, and guidance is provided for taking medications.
- The subsequent visit dates are determined.

11.3.6. Visit 6 (termination visit, 12 months ± 1 week)

At Visit 6, the following procedures will be performed at 12 months ± 1 week after Visit 2.

- Among the demographic survey, only the body weight is measured.
- A physical examination is carried out.
- Vital signs (blood pressure, pulse) are measured.

Confidential Page 30 of 51

- Changes in the medication history and therapeutic potential are checked compared to previous visits.
- Adverse events are checked.
- Abdominal ultrasound is performed. It should be performed prior to the upper gastrointestinal endoscopy and the abdominal CT scan.
- Abdominal CT scan is performed.
- Upper gastrointestinal endoscopy is performed to check the bile reflux.
- A questionnaire to evaluate the symptoms of biliary reflux is prepared.
- Laboratory tests (hematology, biochemistry, urinalysis) are carried out.
- Unused medicinal products are collected, and treatment compliance is checked.

11.3.7. Early Termination Visit

Among randomly assigned subjects, for subjects who meet the early termination or the withdrawal criteria and the study has to terminate before Visit 6, the early termination visit will be conducted. As for the procedures for early termination/dropout, the same test and assessment in accordance with the procedures carried out at Visit 6 (termination visit) will be conducted. However, abdominal ultrasound/abdominal CT scan can be waived if there is an abdominal ultrasound within 3 months prior to an early termination visit or an abdominal CT scan within 6 months prior to the such visit.

- Among the demographic survey, only the body weight is measured.
- A physical examination is carried out.
- Vital signs (blood pressure, pulse) are measured.
- Changes in the medication history and therapeutic potential are checked compared to previous visits.
- Adverse events are checked.
- Abdominal ultrasound is performed. It should be performed prior to the upper gastrointestinal endoscopy and the abdominal CT scan. However, in case of an early termination due to gallstone formation, the test may be waived.
- Abdominal CT scan is performed. However, in case of an early termination due to gallstone formation, the test may be waived.
- A questionnaire to evaluate the symptoms of biliary reflux is prepared.
- Laboratory tests (hematology, biochemistry, urinalysis) are carried out.
- Unused medicinal products are collected, and treatment compliance is checked.

11.3.8. Unscheduled Visit

If there is a need for medical treatment according to the examination results of adverse events and regular visits and the visit was made on a day that is not a regular visit due to changes in the use of the investigational product, follow-up, etc. of adverse events after the clinical study, corresponding information should be recorded in the relevant forms including the case record form. The schedule for regular visits should not change as a result of unscheduled visits.

12. Expected Side Effects and Precautions for Use

Please refer to Appendix 3 Expected Side Effects and Precautions for Use.

13. Discontinuation and Withdrawal Criteria

Confidential Page 31 of 51

13.1. Criteria for Withdrawal from Study

A subject who has signed an informed consent may stop participating in the study at any time during the study period. The reasons for early withdrawal of subjects are as follows:

- 1) Subject's voluntary termination of the study (withdrawal of consent): The investigator confirms that the reason for the withdrawal of consent is not due to adverse events, etc.
- 2) In case of violation of inclusion/exclusion criteria
- 3) If the subject does not visit (failure to follow-up)
- 4) If it is difficult to carry out the study due to adverse events
 : the study may be discontinued at the discretion of the investigator or the subject, regardless of the causal relationship with the investigational product.
- 5) If it is difficult to continue the study at the discretion of the investigator due to the recurrence, etc. of gastric cancer during the study period
- 6) If the study cannot proceed further based on other judgment of the investigator

For subjects who have withdrawn early after randomization, the final evaluation will be conducted according to the schedule for early termination visit regardless of the reason. If they refuse a termination visit or cannot be reached by phone, a call should be made continuously so that all unused investigational products can be returned. The reason(s) for dropout from the clinical study should be recorded in the final assessment section of the case record form.

13.2. Early Termination of Study

Patients who have been confirmed for gallstone formation through the abdominal ultrasound during the post-randomization treatment period should stop participating in the study at the time of confirmation. The final assessment should be performed according to the schedule for visit 6/early termination. The subjects who are terminated early according to the early termination criteria are judged to have completed the study according to the study protocol instead of a dropout.

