10.1. Study Design

This is a multicenter, randomized, double-blinded, placebo-controlled, phase 3 study. Subjects are patients who have been diagnosed with gastric cancer and underwent gastrectomy for treatment. Screening will be conducted on subjects who gave an informed consent to participate in the study. Subjects who meet the inclusion criteria and do not qualify as exclusion criteria will be randomly assigned to DWJ1319 300 mg (DWJ1319 300 mg, once a day), DWJ1319 600 mg (DWJ1319 300 mg, twice a day), or placebo (1: 1: 1). For randomization, stratified randomization using the study site, the lymph node resection range (D1+, D2), and the type of gastrectomy as the stratification factors will be performed and randomization will be performed within 2 weeks from gastrectomy. During the study period, the subjects will visit the study site at screening, randomization (Day 1) and at 3-month interval after the administration of investigational product (at 3, 6, 9, and 12 months) to undergo protocol-specified tests and procedures at each visit. However, any subject with formation of gallstone confirmed during the treatment period will terminate the study at the time of confirmation.

Visit 1	Visit 2	Visit 3	Visit 4	Visit 5	Visit 6
Until Week -2	Day 1	Month 3 ± 1 Week	Month 6 ± 1 Week	Month 9 ± 1 Week	Month 12 ± 1 Week
Screening	Randomizatio n	Treatment period			

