11.1. Clinical Study Schedule

The clinical study is conducted according to the following schedule:

	Screening	Baseline	Treatment			
	Visit 1	Visit 2	Visit 3	Visit 4	Visit 5	Visit 6 / Early Terminatio n ¹⁾
Duration	From Week -2 Day -1	Day 1	Month 3 (±1 week)	Month 6 (±1 week)	Month 9 (±1 week)	Month 12 (±1 week)
Informed consent ²⁾	0					
Demographic survey	0		O ³⁾	O ³⁾	O ³⁾	O ³⁾
Medical/surgical history	0	0				
Physical examination	0			0		0
Vital signs	0	0	0	0	0	0
Inclusion/exclusion criteria	0	0				
Randomization		0				
Abdominal ultrasound ⁴⁾	O ⁵⁾		0	0	0	0
Abdominal CT scan	O ⁵⁾			0		0
Assessment of bile reflux symptoms		0	0	0	0	0
Upper gastrointestinal endoscopy			0			0
Laboratory tests Pregnancy test ⁸⁾	O ⁶⁾		07)	0	07)	0
Prescription of investigational products	_	0	0	0	0	
Treatment compliance			0	0	0	0
Adverse events			0	0	0	0
Prior/concomitant medications ⁹⁾	0	0	0	0	0	0

- 1) For a dropout or early termination, the procedures for Visit 6 will be performed.
- 2) The informed consent form will be obtained in writing prior to study initiation after explaining the objectives and details of the study to the subjects. The informed consent should be obtained prior to any study procedures.
- 3) At the screening visit, the demographic information (subject initials, gender, date of birth, smoking status and alcohol use, weight, height, BMI, etc.) will be collected. Only the body weight is measured at each subsequent visit.
- 4) Will be measured in a fasted state (including the investigational product) on the day of visit. It not in a fasted stated on the day of visit, the test will be conducted by re-visiting during the imaging test window (regular visit ± 2 weeks). A subject with gallstone formation confirmed during the study period will terminate the study at the time of confirmation.
- 5) If there is a recent radiology result (within 6 weeks before screening), the result can be used as a screening test.
- 6) Abdominal CT scan and upper gastrointestinal endoscopy (once in 3 months or 12 months) is a periodic examination that is usually performed in connection with gastrectomy. If there is a result for the corresponding examination, result of the periodic examination shall be collected and utilized.
- 7) If the test result performed during the screening test does not meet the inclusion/exclusion criteria, retesting may be conducted only once.

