14.1. Definition of Analysis Set

14.1.1. Analysis Set for Efficacy Assessment

Both Full Analysis Set (FAS) and Per-Protocol (PP) analyses are carried out for efficacy data, and as a rule, the results of the FAS will be interpreted as the main analysis results.

1) Full Analysis Set (FAS)

Among patients who received at least one dose of the investigational product, those who have not violated the inclusion/exclusion criteria and were subjected to at least one assessment of gallstone formation after randomization.

2) Per-Protocol (PP) Set

The PP Set is composed of subjects who have completed the study without a significant deviation of the protocol that could affect the efficacy of the FAS. The subjects who were terminated according to the early termination criteria of Section 13.2 are included in the PP Set. For subjects who are excluded from the PP Set for other significant deviations, the reasons will be clarified and documented before releasing blinding.

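### Section 13.2 gives completer status only to stones confirmed by ultrasound, so a subject stopped under 10.1 for a stone resting on CT can be dropped from the PP Set because of the outcome

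*Protocol*

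**What the plan says.** Three sets of provisions bear on who stops and who counts as having completed.

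- **When participation ends.** Section 13.2: "Patients who have been confirmed for gallstone formation through the abdominal ultrasound during the post-randomization treatment period should stop participating in the study". Section 10.1 names no imaging method: "any subject with formation of gallstone confirmed during the treatment period will terminate the study at the time of confirmation". The synopsis has the same sentence, and footnote 4 to the schedule in 11.1 agrees: "A subject with gallstone formation confirmed during the study period will terminate the study at the time of confirmation".
- **How a stone is confirmed.** Under 11.2.6 the investigator "obtains pre-contrast and post-contrast abdominal CT images and confirms gallstone formation in the liver, gallbladder, and bile ducts". Section 11.2.7 makes ultrasound the primary test and gives it priority for gallbladder stones when the two tests disagree, but says that "both abdominal ultrasound and abdominal CT should be considered in the case of bile duct gallstones or intrahepatic bile duct gallstones". Of a bile duct stone it adds that it is distinguished on ultrasound "and is determined by compiling the results of abdominal CT scans".
- **Who is a completer.** Section 13.2 treats subjects stopped under its own criterion as having completed, not dropped out. Section 14.1.1 requires completion for the PP Set and then makes one exception: "The subjects who were terminated according to the early termination criteria of Section 13.2 are included in the PP Set". SAP 5.4 repeats both the exception and the ultrasound wording of 13.2.

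**The concern.** The trigger for stopping is wider in 10.1 than in 13.2, but completer status and the PP exception follow the narrower one. A subject whose stone is established with CT while the ultrasound is negative can be stopped under 10.1 without meeting 13.2. No other section makes that subject a completer, and the nearest alternative is the investigator-judgement item among the withdrawal reasons in 13.1.

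Every subject lost by this route has had the event. The exclusion therefore depends on the outcome, which a per-protocol rule should avoid. It also leaves PP membership to whichever section a site follows. The SAP does not close the gap: 6.1.1 counts site-confirmed stones with early termination as events with no limit on imaging method, so the same subject can be an event in the FAS and a non-completer in the PP Set.

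**Working it through.** **Step 1: the sections side by side.** Take a bile duct stone established with the Visit 4 CT when that day's ultrasound is negative.

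| Question | 10.1, synopsis, footnote 4 | 13.2 |
|---|---|---|
| Does participation end? | Yes, the stone is confirmed | No, not confirmed through ultrasound |
| Deemed completer? | Not addressed | Not covered |
| In the PP Set under 14.1.1? | Not by the exception | Yes, if the subject goes on to complete |

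The loss arises only when the site stops the subject under 10.1. Scheduled CTs are at Visits 1, 4 and 6 (11.2.6). A stone found at Visit 6 belongs to a subject who has completed, so the Visit 4 CT is the main source, with any interim routine CT as a minor one.

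**Step 2: the plan's own figure.** With the formula and rates in 8.3:

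N = (1.96 + 0.842)² × (0.07 × 0.93 + 0.18 × 0.82) / 0.11² = 138.01, which agrees with 138 per group.

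At 138 per group the planned rates imply 0.18 × 138 = 24.8 placebo and 0.07 × 138 = 9.7 active stone formers.

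**Step 3: illustration of size.** Let f be the share of all stone formers lost from the PP Set in this way. The documents do not give f. It is assumed equal in both arms, with no other PP exclusions. Then

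- PP rate = p(1 − f) / (1 − pf), and the number left per arm = 138(1 − pf);
- power = Φ(d / s − 1.96), where d is the PP difference and s its unpooled standard error.

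For f = 10%: placebo 0.162 / 0.982 = 16.5%, active 0.063 / 0.993 = 6.3%.

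| f (assumed) | Lost, placebo / active | PP rates | Difference (points) | Power |
|---|---|---|---|---|
| 0% | 0 / 0 | 18.0% vs 7.0% | 11.0 | 80% |
| 5% | 1.2 / 0.5 | 17.3% vs 6.7% | 10.6 | 78% |
| 10% | 2.5 / 1.0 | 16.5% vs 6.3% | 10.2 | 76% |
| 20% | 5.0 / 1.9 | 14.9% vs 5.7% | 9.3 | 71% |

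**Step 4: the planned effect measure.** After the loss, the odds in an arm are p(1 − f) / (1 − p). If f is equal in the two arms it cancels from the unadjusted odds ratio, which stays at (0.07 / 0.93) / (0.18 / 0.82) = 0.34. The downward bias is then in the PP rates and their difference, while the odds ratio loses only precision. It would be biased if f differed between arms.

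**The case against.** The best defence is that 13.2 is the only section written for stopping because of a stone. Stone formation is neither a listed withdrawal reason in 13.1 nor a listed critical deviation in 13.4, so a site would naturally file such a subject under 13.2. Section 14.1.1 includes 13.2 terminations but does not say that other stone terminations are excluded. The route is also narrow: ultrasound is primary, 11.2.7 does not say that CT alone establishes a duct stone, and a subject who continues under the literal 13.2 can complete. All of this makes the case rare, and much of it stands. It does not remove the defect, because 13.2 names its imaging method explicitly, 14.1.1 cites 13.2 by number, and completion is a condition of the PP Set.

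Three stronger readings are tempting but not supported.

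- A reader might infer that a duct stone suspected on ultrasound at Visit 3 or 5, where no CT is scheduled, is also lost, because 11.3.7 says: "Abdominal CT scan is performed. However, in case of an early termination due to gallstone formation, the test may be waived". But 13.2 requires confirmation, not suspicion. A subject stopped under 13.2 is a deemed completer and stays in the PP Set, and SAP 6.1.1 counts the event regardless of the external assessment.
- A reader might take the PP analysis to be the only check on the FAS result. Section 14.4.2 also analyses investigator-assessed stones and time to stone formation, and SAP 8.4.1 names a three-group model as a sensitivity analysis.
- A reader might infer that the primary conclusion is at risk. Section 14.1.1 makes the FAS the main analysis, and FAS membership does not require completion.

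**Conclusion.** The inconsistency is real, and its consequence for the PP Set follows from the literal text. It is minor. It touches only the PP analysis, and chiefly stones that rest on the Visit 4 CT. The likely effect is a modest downward bias in the PP event rates and the PP difference.

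The size rests on an assumed share. Because only stones found before Visit 6 can be lost, while the share is applied to all stones through 12 months, the upper end of the 5% to 20% range would need a large CT-based fraction among the earlier stones. Nothing in the documents supports a particular value.

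**What to change.** Two wording changes, made before unblinding.

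1. Reconcile 10.1 (with the synopsis and footnote 4), 11.2.7, 11.3.7 and 13.2 so that one statement says what counts as a confirmed stone that ends participation. Which clinical or imaging rule that should be is for the sponsor and the investigators; this point takes no position on it.
2. In 14.1.1 and SAP 5.4, word the PP exception so that every subject terminated because of a stone confirmed under the reconciled definition counts as a completer and stays in the PP Set, absent another significant deviation. The extract of 13.2 reproduced in SAP 5.4 should be updated to match.

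The cost is a few lines in the protocol and one paragraph in the SAP. The change to the PP exception needs no extra visits or data and does not alter the primary analysis.
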